5.4 OTHER VARIABLE(S)

Demographic and baseline characteristics

- Sex: Male, Female
- Age [years]
Actual age based on first administration of Trazenta[®] (or other oral antidiabetic drug)
- Age categories 1: ≤50 years, 51 to 64 years, 65 to 74 years, ≥75 years
- Age categories 2: <65 years, ≥65 years
- Height [cm]
- Body weight [kg]
- Body weight categories: ≤50 kg, >50 to 70 kg, >70 to 90 kg, >90 kg
- Body mass index (BMI) [kg/m²]
 $BMI [kg/m^2] = weight [kg] / (height [m])^2$
- BMI categories 1: <25 kg/m², 25 to <30 kg/m², ≥30 kg/m²
- BMI categories 2: <25 kg/m², ≥25 kg/m²
- BMI categories 3: <30 kg/m², ≥30 kg/m²
- Waist circumference [cm]
- Renal dysfunction : estimated glomerular filtration rate (eGFR) [mL/min/1.73m²]
- eGFR categories 1: ≥90 mL/min/1.73m²(Normal), 60 to <90 mL/min/1.73m²(Mild), 30 to <60 mL/min/1.73m²(Moderate), 15 to <30 mL/min/1.73m²(Severe), <15 mL/min/1.73m² (Endstage)
- eGFR categories 2: ≥60 mL/min/1.73m², <60 mL/min/1.73m²
- Hepatic dysfunction categories 1: (>ULN [35 U/L] of AST, >ULN of ALT [35 U/L], >ULN of total bilirubin [17 umol/L], or >ULN of AL P [120 U/L]), or other
In case > ULN of AST and CK increase (>400 U/L), patients do not include in hepatic dysfunction.

Conversion factors:

$$\text{For total bilirubin: } 17.102787754404 \times [\text{mg/dL}] = [\text{umol/L}]$$

For AST, ALT, ALP: [IU/L] = [U/L]

- Hepatic dysfunction categories 2: $\leq 1*ULN$, $>1*ULN$ to $\leq 2*ULN$, $>2*ULN$ to $\leq 3*ULN$, $>3*ULN$
 - Note: worst value of AST, ALT, total bilirubin, or ALP will be used for the categorization
- Hepatic dysfunction categories 3: (Yes, No, Unknown)
 - Hepatic disorders (Narrow) (SMQ 20000005)
 - Biliary disorders (Narrow) (SMQ 20000118)
 - Note: Presence at baseline is yes
- Patient status: (In patient, Out patient)
- Indication (Type II diabetes mellitus, Other)
- Smoking status (Never, Ex-smoker, Smoker, Unknown)
- Duration of diabetes (≤ 1 years, >1 to 5 years, >5 years, Unknown)
[First administration of Trazenta[®] (or other oral antidiabetic drug) – first diagnosis of type 2 diabetes mellitus + 1 (if negative value due to the missing and imputation, then 1)] / 365.25
- Hypersensitivity factor (Yes, No, Unknown)
- Concomitant diagnosis (Yes, No, Unknown)
- Cardiovascular (SMQ) history (Yes, No, Unknown)
 - Ischemic heart disease (SMQ: 20000043)
 - Cardiac failure (SMQ: 20000004)
 - Cerebrovascular disorders (SMQ: 20000060)
 - Torsade de pointes/QT prolongation (SMQ: 20000001)

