 - Note: regardless of presence at baseline
- Baseline HbA1c [%] (based on NGSP)
- Baseline HbA1c categories: $<7.0\%$, 7 to $<8\%$, 8 to $<9\%$, $\geq 9\%$
- Baseline FPG [mg/dL]
- Baseline FPG categories: <126 mg/dL, 126 to <140 mg/dL, 140 to <200 mg/dL, ≥ 200 mg/dL
- Prior antidiabetic medication at baseline (For TRZ group):[\(See Table 5.4: 1\)](#)
 - Prior antidiabetic medication at baseline 1 (Yes, No, Unknown)
 - Prior antidiabetic medication at baseline 2 (only, combination with other DM medication, none)
 - Sulfonylurea (only, combination with other DM medication, none)
 - Biguanide (only, combination with other DM medication, none)
 - Thiazolidinedione (only, combination with other DM medication, none)
 - Alpha-glucosidase inhibitor (only, combination with other DM medication, none)
 - DPP-IV inhibitor (except Linagliptin) (only, combination with other DM medication, none)
 - Glinide (only, combination with other DM medication, none)
 - SGLT2 inhibitor (only, combination with other DM medication, none)
 - Insulin (only, combination with other DM medication, none)
 - GLP-1 receptor agonist (only, combination with other DM medication, none)

- Anti-diabetic medication categories (for other OAD group): sulfonylurea, biguanide, thiazolidinedione, alpha-glucosidase inhibitor, DPP-IV inhibitor, glinide, other)

Table 5.4: 1 Categories for antidiabetic medication based on Nihon-iyakuhinshu

Class	Medication name	Code
Sulfonylurea		First 4 numbers = 3961
Biguanide		First 4 numbers = 3962
Thiazolidinedione	PIOGLITAZONE HYDROCHLORIDE	First 7 numbers = 3969007
Alpha-glucosidase inhibitor	ACARBOSE	First 7 numbers = 3969003
	VOGLIBOSE	First 7 numbers = 3969004
	MIGLITOL	First 7 numbers = 3969009
DPP-IV inhibitor	SITAGLIPTIN PHOSPHATE HYDRATE	First 7 numbers = 3969010
	VILDAGLIPTIN	First 7 numbers = 3969011
	ALOGLIPTIN BENZOATE	First 7 numbers = 3969012
	LINAGLIPTIN	First 7 numbers = 3969014
	TENELIGLIPTIN HYDROBROMIDE HYDRATE	First 7 numbers = 3969015
	ANAGLIPTIN	First 7 numbers = 3969016
	SAXAGLIPTIN HYDRATE	First 7 numbers = 3969017
	TRELAGLIPTIN SUCCINATE	First 7 numbers = 3969024
	OMARIGLIPTIN	First 7 numbers = 3969025
Glinide	NATEGLINIDE	First 7 numbers = 3969006
	MITIGLINIDE CALCIUM HYDRATE	First 7 numbers = 3969008
	REPAGLINIDE	First 7 numbers = 3969013
SGLT2 inhibitor	IPRAGLIFLOZIN	First 7 numbers = 3969018
	DAPAGLIFLOZIN	First 7 numbers = 3969019
	LUSEOGLIFLOZIN	First 7 numbers = 3969020
	TOFOGLIFLOZIN	First 7 numbers = 3969021

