6.3 PATIENT SETS ANALYSED

The following two analysis sets are defined as in CTP Section 7.3. The safety set will be the basis of all demographic, baseline and safety analyses. Efficacy analysis will be on basis of the efficacy set.

[figure not shown]
- Safety set:
This patient set includes all patients who had no invalid registration, who were dispensed Trazenta® and were documented to have taken at least one dose of Trazenta®. Patients with CRF data which were not ensured by the investigator will be excluded from this patient set.

[figure not shown]
Proprietary confidential information © 2017 Boehringer Ingelheim International GmbH or one or more of its affiliated companies

[figure not shown]
- **Efficacy set:**
This patient set includes all patients with Trazenta[®] in the safety set who have at least one available on-treatment HbA1c value.

Additional analysis set is defined for comparing the baseline date between Trazenta[®] group and other group:

- **Baseline set:**
This patient set includes all patients who had no iPV leading to exclude from baseline set (i.e., category “Baseline”).

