7.1 DEMOGRAPHIC AND OTHER BASELINE CHARACTERISTICS

Descriptive statistics for the demographic and other baseline characteristics described in [Section 5.4](#) are planned by treatment groups (Trazenta[®] or others). Absolute standard difference (ASD) will be also calculated based on the following formulas. (1)

For binary variable:

$$ASD = \left| \frac{(\hat{p}_{TRZ} - \hat{p}_{OAD})}{\sqrt{\frac{\hat{p}_{TRZ}(1 - \hat{p}_{TRZ}) + \hat{p}_{OAD}(1 - \hat{p}_{OAD})}{2}}} \right|$$

For continuous variable:

$$ASD = \left| \frac{(\bar{x}_{TRZ} - \bar{x}_{OAD})}{\sqrt{\frac{s_{TRZ}^2 + s_{OAD}^2}{2}}} \right|$$

ASD > 0.1 is considered to be statistically meaningful difference.

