7.2 CONCOMITANT DISEASES AND MEDICATION

Concomitant diseases will be coded by the latest version of Medical Dictionary for Regulatory Activities (MedDRA). Frequency of patients will be summarised by treatment (Trazenta[®] or others), SOC and PT.

Concomitant medication will be coded by latest version of “Nihon-iyakuhinshu”.

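### SAP 5.4 restricts prior antidiabetic medication to the Trazenta group, so the between-group baseline table as written has no comparator column or ASD for naïve versus previously treated status or prior drug class

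*SAP*

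**What the plan says.** SAP 6.3 creates a Baseline set for one purpose: "Additional analysis set is defined for comparing the baseline date between Trazenta" and the other group. SAP 7.1 then plans "Descriptive statistics for the demographic and other baseline characteristics described in" Section 5.4, by treatment group, and adds: "Absolute standard difference (ASD) will be also calculated based on the following formulas". One formula is for binary variables and one for continuous variables. The reading rule is "ASD > 0.1 is considered to be statistically meaningful difference".

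In SAP 5.4, prior therapy appears under "Prior antidiabetic medication at baseline (For TRZ group"). That block holds a Yes/No/Unknown item for any prior antidiabetic drug and nine class items, each with three levels: the only drug, in combination, or none. The comparator group has a different entry, "Anti-diabetic medication categories (for other OAD group"), followed by seven class labels.

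On the protocol side, the other-OAD flow chart and Section 6.2.1 both list the pre-treatment drug among the baseline items for the other-OAD group. Section 7.3 plans baseline descriptive statistics for both groups, and Section 7.6 extends them to every baseline characteristic of the other-OAD group. SAP 4 states that nothing has changed from the protocol's planned analysis.

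**The concern.** The other-OAD group, 1,500 planned patients, has no observation period; baseline data are all it contributes. Protocol 2.1 says it is included so that differences in patient characteristics between drugs can be assessed. Whether a patient is naïve or previously treated, and with what, is an obvious characteristic to show side by side.

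A programmer following SAP 5.4 literally would fill those rows for Trazenta and leave the comparator column out. The reader could not then apply the SAP's own 0.1 flag to prior therapy.

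**Working it through.** The plan states no figure on this point, so there is none to reproduce. The check is a comparison of texts.

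1. **What feeds the table.** SAP 7.1 names Section 5.4 as its source. A variable defined there for one group only has no second column and no ASD.

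2. **Is the restriction a general habit of wording?** No. Age in SAP 5.4 begins "Actual age based on first administration of Trazenta" and then adds the other oral drug in parentheses. Diabetes duration is defined the same way. Where both groups were meant, the section says so.

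3. **Does the other-OAD list fill the gap?** No.
   - Trazenta block: nine classes (sulfonylurea, biguanide, thiazolidinedione, alpha-glucosidase inhibitor, DPP-IV inhibitor, glinide, SGLT2 inhibitor, insulin, GLP-1 receptor agonist).
   - Other-OAD list: seven labels, namely the first six of those plus a residual category. So 9 − 6 = 3 classes have no label of their own.
   - The list has no level for no prior drug and none for unknown, so it cannot code naïve status under any reading.
   - Protocol 6.2.1 collects the name of the other oral drug as an item separate from the pre-treatment drug. The list fits the former.

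4. **Does another SAP section fill it?** SAP 7.2 plans a frequency table by treatment group for concomitant diseases, but for drugs it gives only the dictionary: "Concomitant medication will be coded by latest version of" the Japanese drug list. No other visible section summarises prior therapy for the other-OAD group.

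5. **Would the data exist?** Yes. The pre-treatment drug is a baseline item in both groups.

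6. **Does the protocol call for the column?** Yes, as description. Protocol 7.6 covers all baseline characteristics of the other-OAD group, and SAP 4 withdraws nothing.

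7. **Extent.** One item for any prior drug plus nine classes gives 1 + 9 = 10 yes/no rows without a comparator column. The block could be counted as 11 variables if the line ending in 2 is a variable of its own. It carries the same levels as the nine class lines and may be only their heading. The ten rows do not depend on this.

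**The case against.** The best defence is that the SAP presents itself as an elaboration of the protocol and declares no change, so the commitment in Protocol 7.6 survives and the column may be produced anyway. That is possible. But an explicit restriction in the SAP then conflicts with the protocol section it elaborates, which is a reason to correct the wording. SAP 6.4 and 7.6 are redacted, and the analysis data set plan mentioned in SAP 6.1 is not public. Any of these might hold more, so the point is confined to visible text.

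A reader might also infer more than the documents support:

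- *That the missing ASD breaks a protocol commitment.* It does not. The protocol plans descriptive statistics only; the ASD is the SAP's addition. The departure from the protocol is the missing descriptive column.
- *That the objective names prior therapy as a comparison variable.* In Protocol 2.2 the naïve-or-switched phrase is a parenthesis describing who enters, and it mirrors the inclusion criterion. The firmer support is Protocol 7.6.
- *That the three-level class items cannot have an ASD.* SAP 7.1 has no multi-category formula, but this applies equally to age categories, smoking status and diabetes duration, and the binary formula can be used level by level. It is not a defect of this block.
- *That the groups are imbalanced on prior therapy.* The documents give no share of naïve patients in either group, so nothing can be said about this.

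**Conclusion.** The point holds as a minor one. On the visible text, SAP 5.4 and 7.1 together leave the other-OAD group without any summary of naïve versus previously treated status or prior drug class, and so leave the comparison and its ASD undefined. The Trazenta column itself is planned; what is missing is its counterpart. This is a stated restriction at odds with Protocol 7.6, not merely a detail left open.

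The effect is limited to ten rows of a descriptive comparison. Safety and efficacy analyses use Trazenta patients only and do not change. The conclusion rests on two readings: that the table contains what SAP 5.4 defines, as SAP 7.1 says, and that the redacted and unpublished material does not supply the column. It does not depend on how the other-OAD list is read, because that list lacks an untreated level either way.

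**What to change.** In SAP 5.4, remove the restriction to the Trazenta group and define the following identically for both groups in the Baseline set:

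1. **Any prior antidiabetic drug:** Yes/No/Unknown. Prior linagliptin in an other-OAD patient counts as Yes.
2. **Each of the nine prior classes:** yes/no, with sole use and use in combination both counted as yes. Apply the SAP 7.1 binary ASD to these rows and to item 1.
3. **DPP-IV row:** in the between-group table use the full class in SAP Table 5.4: 1, including linagliptin, and footnote the number with prior linagliptin. The present exclusion of linagliptin would code an other-OAD patient switched from it as no. The Trazenta column should be unaffected, since code A1.2 in SAP Table 6.2: 1 excludes prior Trazenta users from the Baseline set.
4. **Denominators:** show percentages on the SAP 7 default (all patients in the set, Unknown as its own level). If the ASD uses known values only, say so in a footnote.
5. **Other-OAD list:** label it as the class of the drug being started, if that is what is meant.

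The cost is a few words in SAP 5.4, one collapsing rule, two footnotes and ten indicators coded for the other-OAD group from data already to be collected. No analysis set changes.

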6. GENERAL ANALYSIS DEFINITIONS

6.1 TREATMENT(S)

For basic study information on treatments, please refer to CTP Section 4. The technical specification for treatment set-up is described in the analysis data set (ADS) plan.

For efficacy analyses, data up to 7 days after last treatment intake will be considered as on treatment for HbA1c [REDACTED]. For safety analyses, data up to 7 days after last treatment intake will be considered as on treatment for AE.

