## 5.2 SAFETY

### 5.2.1 Endpoints of safety

- Incidence of adverse drug reactions (ADRs)
- Incidence of serious adverse events (SAEs)

- [REDACTED]

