##### Serious adverse event

A SAE is defined as any AE which results in death, is immediately life-threatening, results in persistent or significant disability / incapacity, requires or prolongs patient hospitalisation, is a congenital anomaly / birth defect, or is to be deemed serious for any other reason if it is an important medical event when based upon appropriate medical judgment which may jeopardise the patient and may require medical or surgical intervention to prevent one of the other outcomes listed in the above definitions.

An AE which possibly leads to disability will be reported as an SAE. Every new occurrence of cancer will be reported as a SAE regardless of the duration between discontinuation of the drug and the occurrence of the cancer.

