#### 5.2.2.2 Adverse event and serious adverse event reporting

All AEs, serious and non-serious, occurring during the course of the PMS will be collected, documented and reported to the sponsor by the investigator on the appropriate CRFs. Reporting will be done according to the specific definitions and instructions detailed in the 'Adverse Event Reporting' section of the site materials (that include all necessary documents, the protocol, instructions for conducting PMS, the package insert etc.).

For each AE, the investigator will provide the onset, end, intensity, outcome, seriousness and action taken with Trazenta® Tablets. The investigator will determine the relationship of Trazenta® Tablets to all AEs as defined in the 'Adverse Event Reporting' section of the site materials.

The investigator has the responsibility to report AEs during the specified observational phase.

Any SAE, whether or not considered related to Trazenta® Tablets, or whether or not Trazenta® Tablets has been administered, must be reported immediately via EDC system or by a NBI MR. Further details regarding this reporting procedure are provided in the site materials.

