### 6.2.3 End of trial and follow-up period

Trazenta® Tablets:

The visit at 156 weeks after starting Trazenta® Tablets treatment or the last visit before discontinuation will be the end of the PMS. There is no follow-up period.

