7.8 SAFETY ANALYSIS

7.8.1 Adverse events

Unless otherwise specified, the analyses of adverse events (AEs) will be descriptive in nature. All analyses of AEs will be based on the number of patients with AEs and NOT on the number of AEs.

Furthermore, for analysis of AE attributes such as duration, severity, etc. multiple AE occurrence data on the case report form, will be collapsed into AE episodes provided that all of the following applies:

- The same MedDRA lowest level term was reported for the occurrences
- The occurrences were time-overlapping or time-adjacent (time-adjacency of 2 occurrences is given if the second occurrence started on the same day or on the day after the end of the first occurrence)
- Treatment did not change between the onset of the occurrences OR treatment changed between the onset of the occurrences, but no deterioration was observed for the later occurrence

For further details on summarization of AE data, please refer to the guideline 'Analysis and Presentation of Adverse Event Data from Clinical Trials' ([3](#)).

AE analyses will be carried out after integrating AE data from CRF and AE data from perceive system.

In addition, AEs coded as “no adverse event” will not be included in the AE analyses.

An overall summary of adverse events will be presented. This will be also made for patients who added patients not treated as mono therapy at baseline to safety set (i.e. all patients with Trazenta® treatment).

The frequency of patients with ADRs, with serious AEs, with AEs leading to discontinuation, and with AEs leading to death will be summarised by treatment, primary SOC and PT. AEs and ADRs will also be reported by intensity.

To compare risks of overall ADR in different patient subgroups, frequency tabulation stratified by different patient subgroups will be provided with odds ratios and exact 95% confidence intervals whenever specified (see [Section 6.4](#)). Logistic regression will be used for odds ratio.

In addition, summaries for the time to onset of first episode for the ADRs will be tabulated, by duration (>0 to 12 weeks, >12 to 26 weeks, >26 to 40 weeks, >40 to 52 weeks, >52 to 64 weeks, >64 to 78 weeks, >78 to 104 weeks, >104 to 130 weeks, >130 to 156 weeks, >156 weeks), by treatment, primary SOC, and PT.

An ADR is defined as an AE for which either the investigator or the sponsor (or both) assess the causal relationship to Trazenta® either as “Related,” “Probably related,” or “Cannot be

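### Does a new cancer that starts after the drug is stopped fall between the protocol's reporting rules and the SAP's 7-day window?

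*SAP*

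**What the plan says.** Four places bear on a cancer that starts after linagliptin is stopped.

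- **Protocol 5.2.2.1, definition of a serious adverse event.** "Every new occurrence of cancer will be reported as a SAE regardless of the duration between discontinuation of the drug" and the onset of the cancer. This rule has no time limit.
- **Protocol 5.2.2.2, repeated in 8.4.1 (Time windows).** "The investigator has the responsibility to report AEs during the specified observational phase". A separate paragraph follows in both sections. It requires immediate reporting of any SAE, related or not and whether or not the drug was given, through the EDC system or a company medical representative. It states no time limit and leaves further detail to the site materials.
- **Protocol 6.2.3.** The week 156 visit or "the last visit before discontinuation will be the end of the PMS. There is no follow-up period".
- **SAP 6.1.** "For safety analyses, data up to 7 days after last treatment intake will be considered as on treatment for AE".

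SAP 7.8.1 describes the tables: "The frequency of patients with ADRs, with serious AEs, with AEs leading to discontinuation, and with AEs leading to death will be summarised" by treatment, system organ class and preferred term. On data sources it says: "AE analyses will be carried out after integrating AE data from CRF and AE data from perceive system". It refers to an in-house guideline for further detail on summarising AEs. Part of 7.8.1 and the whole of 6.4 are redacted in the public copy.

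**The concern.** Take a patient who stops the drug and has a cancer diagnosed one month later. The SAE definition makes it reportable. The general reporting duty covers only the observational phase, which for this patient has ended, and no follow-up visit exists at which to collect it. SAP 6.1 classes it as off treatment. It could still reach the database, because the SAP merges CRF data with a second AE source and the visible text sets no time limit on that merge.

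SAE incidence is one of the safety endpoints named in Protocol 5.2.1. If sites read the reporting sections differently, late cancers would be captured unevenly. If the SAP does not say whether the SAE table holds only on-treatment events, a reader of the report could not tell whether a late cancer is in the table, left out, or shown elsewhere. The 7-day window is also short against the time that remains after an early stop, so a cancer found after stopping would usually lie outside it.

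**Working it through.** **1. The plan's own figure.** Protocol 7.6, read without the struck-out values, asks for 1,500 patients so that at least one case of a reaction with incidence 0.2% (or 0.31%) is seen with probability 95% (or 99%). With n = ln(1 − C) / ln(1 − p):

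- p = 0.002, C = 0.95: n = 1,497; at 1,500 the probability is 1 − 0.998^1500 = 95.04%.
- p = 0.0031, C = 0.99: n = 1,484; at 1,500 the probability is 1 − 0.9969^1500 = 99.05%.

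The sample size is reproduced, and nothing in the concern affects it.

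**2. How short the window is.** The documents give no discontinuation rate, so the stopping times here are assumed. Days left to week 156 = (156 − stop week) × 7; share covered = 7 / days left.

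| Stop at week | Days left | Share within 7 days |
|---|---|---|
| 12 | 1,008 | 0.7% |
| 26 | 910 | 0.8% |
| 52 | 728 | 1.0% |
| 78 | 546 | 1.3% |
| 104 | 364 | 1.9% |

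A cancer reported after stopping could therefore easily start after day 7. That premise of the concern is sound.

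**3. Do the rules give three limits?** They do different jobs.

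| Place | What it governs | Time limit |
|---|---|---|
| Protocol 5.2.2.1 | Which events count as SAEs | None for new cancer |
| Protocol 5.2.2.2 and 8.4.1, general sentence | The investigator's duty for all AEs | Observational phase |
| Protocol 5.2.2.2 and 8.4.1, SAE paragraph | Urgency and route for SAEs | None stated |
| Protocol 6.2.3 | End of scheduled observation | Week 156 or last visit before stopping |
| SAP 6.1 | The label on-treatment | Last intake plus 7 days |

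The SAP row is not a reporting limit. It attaches a label, and no visible sentence says that events without the label are dropped. What remains is a tension inside the protocol, between the cancer rule and the general duty. The SAE paragraph largely settles it: the definition makes a late cancer an SAE, SAEs have a stated route with no end date, and the site materials carry the instructions. A specific rule placed beside a general one is an ordinary construction.

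**4. What one late case would do.** The single case is assumed for illustration. One patient in 1,500 is 1/1,500 = 0.067 percentage points. For a cancer term with no other case, the exact one-sided 95% upper limit is:

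- 0/1,500: 1 − 0.05^(1/1500) = 0.1995%
- 1/1,500: the 0.95 quantile of Beta(2, 1499) = 0.3159%

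The two-sided 95% upper limits are 0.246% and 0.371%. The visible SAP plans no confidence interval for SAE incidence, so these figures only give a sense of scale.

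**The case for a change.** The strongest case for a change runs as follows. Protocol 8.4.1 is headed as the section on time windows, so it is where a site would look for an exception, and it gives none for cancer. The SAE paragraph can be read as setting urgency only: its clause on whether the drug was given is about exposure, not about time. The protocol never says that the cancer rule overrides the observational phase. On the SAP side, counts are of patients in the safety set, so a late cancer placed in the SAE table would come from a period without systematic observation, while one left out and not listed would be invisible. A sentence in each document would cost little.

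Part of this stands. The protocol wording is not tidy, and the visible SAP does not say where an event starting after day 7 appears. Three things weaken it as a reason for change.

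- Uneven reporting between sites is conjecture, because sites work from instructions that are not in these documents.
- Incomplete capture of late cancers comes from the absence of follow-up. New wording would not create the missing observation time.
- Nothing in the documents decides between including late cancers in the SAE table and listing them apart. Protocol 5.2.1 does not restrict the SAE endpoint to on-treatment events, so a rule keeping them out would be a preference. If presentation after day 7 is open, it is open for every AE and not only for cancer.

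**Conclusion.** No change is needed. This is missing detail that analysts can fill sensibly: no stated rule is shown to produce a wrong result. A late cancer has a route into the data, and SAP 6.1 supplies the definition needed to label it post-treatment. Whether it then appears in the SAE table with a note or in a separate listing can be decided from data already reported.

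The effect cannot be estimated from the documents and is probably small: 0.067 percentage points for each late case among 1,500 patients, in an analysis that Protocol 7.2 describes as descriptive and exploratory. Expedited reporting (Protocol 8.4.2) and periodic safety reports (Protocol 2.1) run separately and are unaffected.

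The conclusion rests on two assumptions: that the SAE paragraph is read as having no time limit, and that neither the site materials nor the unseen SAP sources contain a contrary rule. If the first failed, late cancers would be reported less completely, but they have no systematic follow-up behind them in any case and could not support an incidence.
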